### Preliminary/background data:

Our prior research and clinical data prior to collaboration with BRANY IRB may be read in the published article int the following link: <https://link.springer.com/content/pdf/10.1007/s00403-024-03423-0.pdf>.

“Our research presents an innovative approach to treating basal and squamous cell carcinomas through the combination of fractional laser therapy and tirbanibulin ointment. Since the treatment of our first participant, we have observed 100% clinical and/or histological clearance of lesions in all subjects over one year. The joint action of both the thulium and erbium lasers, bulk heating with a heat shock response, and the predicted improved penetration of the tirbanibulin ointment demonstrates an effective strategy for the destruction of these cancerous cells. In addition, the feld effect of the treatment may decrease the risk of recurrence and adjacent cancers in the future. This study holds the potential to positively impact nearly 5 million Americans annually who suffer from basal and squamous cell carcinomas. The advantages of laser treatment, including the absence of scarring and bleeding, quick healing, and non-invasiveness, address the specific needs of various patient populations. In conclusion, the findings of this study ofer a groundbreaking and patient-centric solution for basal and squamous cell carcinoma treatment. The possibility to improve the lives of millions paves the way for a paradigm shift in skin cancer management.”

“Fractional laser skin treatment is associated with a relatively low complication rate. Side effects and complications observed in this study were temporary and did not result in long-term or significantly severe sequelae (e.g., scarring).” Per: Gruber EM, Tanzi EL, Alster TS. Side effects and complications of fractional laser photothermolysis: experience with 961 treatments. *Dermatol Surg.* 2008 Mar;34(3):301-5; discussion 305-7. doi: 10.1111/j.1524-4725.2007.34062.x. Epub 2008 Jan 8. PMID: 18190541.

### Rationale

Basal cell carcinomas (BCC) and squamous cell carcinomas (SCC) are the most common forms of cancer in the United States. The current most commonly accepted treatments for SCCs and BCCs depending on the location and depth, are surgical removal, electrodesiccation and curettage, or Mohs surgery. Although these treatments were created to limit the destruction of surrounding healthy cells, all treatments typically leave a scar. Tirbanibulin ointment is one of the leading topical medications for the treatment of actinic keratoses, which can progress into SCCs and less commonly into BCCs. Studies have found that non-ablative fractional laser therapy can be an effective treatment for actinic keratoses. Researchers have also tested the treatment of keratinocyte carcinomas with varying laser types and results. However, in this study we have carefully selected the laser type, settings, and treatment design, and have incorporated the use of tirbanibulin ointment, predicting a field effect response and increased depth of penetration.

### Study Objective

We seek to evaluate the effectiveness of fractional laser therapy and tirbanibulin ointment to treat squamous and basal cell carcinomas. We will execute this by using both thulium and erbium lasers on previously biopsy-confirmed SCCs and BCCs and applying bulk heating methods. Then, depending on the level of invasiveness, instruct subjects to apply the ointment over the course of five nights immediately following the treatment. The intention of this study

is to minimize the need for invasive surgical procedures so as to optimize the cosmetic appearance, and provide a treatment option that is beneficial for a wide range of individuals.

**Design, Selection Criteria, Data Source**

**Study design:** Longitudinal, forward directed, interventional

**Study type:** prospective

**Methodology:** site-based ([name] private practice dermatology office)

**Patient population:** The dermatology office is located in New York, NY but patients may come from any origin.

The patient population consists of any patient, new or established, of [name]. Patients must have a biopsy confirmed BCC and/or SCC skin cancer confirmed by a dermatopathologist either under the care of [name] or another physician.

**Expected study duration:** Approximately 5 years. To ensure the clearance of skin cancer, we will track our patients for at least 5 years. All patients with a history of skin cancer, including those in this study, are carefully monitored and instructed to return for biannual skin exams or earlier if they notice any abnormalities at the site of the treatment.

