**\*\*For nodular/invasive carcinomas:**

**-Night of Visit #1: At home ointment application to treated site**

**-Night #2- Night #5: At home ointment application to treated site**

-For approximately 10-14 days following completion of ointment application: At home wound care performed twice a day at the treated site. Patients instructed to complete wound care until site is completely healed (for some could take up to 1 month)

1 month post-tx: Follow-up to check site (Take biopsy per patient consent)

6 month post-tx: Follow-up for complete skin exam and to check site

1 year: Follow-up for complete skin exam and to check site (Take biopsy per patient consent)

1.5 year: Follow-up for complete skin exam and to check site

2 years: Follow-up for complete skin exam and to check site (Take biopsy per patient consent)

2.5 year: Follow-up for complete skin exam and to check site

3 year: Follow-up for complete skin exam and to check site (Take biopsy per patient consent)

3.5 year: Follow-up for complete skin exam and to check site

4 year: Follow-up for complete skin exam and to check site (Take biopsy per patient consent)

4.5 year: Follow-up for complete skin exam and to check site

5 year: Follow-up for complete skin exam and to check site (Take biopsy per patient consent)

\*\*Advise biannual skin exam thereafter (always recommended to any patients with history of SCC/BCC skin cancer)

\*\*Advise return to office ASAP if abnormalities occur at site at any point in time

**Patient recruitment:** Established patients will be recruited if they develop biopsy confirmed SCC or BCCs. They will be given the option to participate in the study. For new patients, recruitment will be based on referrals by current patients or other physicians. Additionally, new patients may be recruited through the office website, social media, or other online marketing conducted by employees of [name].

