**Data Collection/Data Management, Quality Control of Data**

-All data will be tracked by [name] and his medical assistants

-Detailed visit information, treatment and follow-up notes will be documented through the EMR program

Macpractice and we will utilize other data management methods such as google sheets

-Any missing data will be accordingly documented

-Missing data will be noted in results section/ likely to be reported in a table format

-Data will be collected at the initial treatment including patient demographics, location of lesion, invasiveness of carcinoma and treatment settings. Each subsequent follow up visit will include data in the format of “clinical recurrence or no clinical recurrence of carcinoma” at each follow-up visit. If a biopsy is taken and is clear then “no histological recurrence” will be reported. If the biopsy shows evidence of carcinoma, then the detailed pathological results will be reported. Any additional necessary data including complications will be tracked and reported.

-Written consent will be obtained by each patient prior to treatment and scanned electronically into their EMR patient file.

-Thermal data and images will be collected through TopDon thermal imaging camera application on an IPad, then exporting in graph form to google sheets.

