**Statistics**

-Subgroups will be defined by cancer type, cancer invasiveness, skin type, and gender

- The sample size is likely to be 20-100 participants as estimated by the established patients at the office of [name] MD and the frequency of carcinoma diagnosis.
- On a per-case basis, treatment is considered effective if there is no clinical/histological recurrence in 5 years.
- For the study as a whole, the treatment is considered effective if the recurrence rate is lower or approximately equal to the comparison groups: other FDA approved/traditional treatment options. For example, studies have shown that after surgical excision, over 5 years, superficial BCC recurrence rate is between 2% and 5%, nodular BCC 2-8%, SCC in situ ~0.8%, and invasive SCC between 1.7% and 6.4%. And, most surgical excision recurrences occur within 2 years. Other methods such as electrodessication and curettage have higher recurrence rates. So, we would consider our treatment successful if our recurrence rates are lower or approximately equal to any of the approved treatment options.
- Treatment is not randomized. Participation is determined by the patient's willingness to participate. If they participate they are given the treatment. No placebos or control groups.

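### The stated study duration of about 5 years holds only as follow-up per patient, and the yes/no 5-year rule cannot place recurrence-free lesions withdrawn before year 5 in the recurrence rate (minor)

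*Protocol*

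**What the plan says.** **Duration.** Protocol, Design, Selection Criteria, Data Source, under expected study duration: "Approximately 5 years. To ensure the clearance of skin cancer, we will track our patients for at least 5 years". The visit schedule agrees with this for each patient. Its last entry reads "5 year: Follow-up for complete skin exam and to check site (Take biopsy per patient consent".

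**Recruitment.** The patient recruitment paragraph has people entering as cancers arise: "Established patients will be recruited if they develop biopsy confirmed SCC or BCCs". Statistics ties the expected 20-100 participants to how often carcinoma is diagnosed. No accrual period is given.

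**Success rules.** For the single case, Statistics says: "On a per-case basis, treatment is considered effective if there is no clinical/histological recurrence in 5 years". For the study it says: "So, we would consider our treatment successful if our recurrence rates are lower or approximately equal to any of the approved treatment options". The benchmarks are 5-year figures: "studies have shown that after surgical excision, over 5 years, superficial BCC recurrence rate is between 2% and 5" (per cent), then 2-8% for nodular BCC, about 0.8% for SCC in situ and 1.7-6.4% for invasive SCC. It adds that "most surgical excision recurrences occur within 2 years".

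**Withdrawal.** Potential bias names attrition as a risk. The Ethics section classes patients who cannot be reached as withdrawn and records this. Data Collection says that missing data will be documented and reported. None of these places says how a withdrawn, recurrence-free lesion counts in the rate.

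**The concern.** Two statements do not do the work asked of them.

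First, a study that enrols over time and follows everyone for at least 5 years cannot finish in about 5 years unless enrolment is almost instantaneous. Read as total study time, the label conflicts with the sentence that follows it.

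Second, the per-case rule has two outcomes but needs 5 years of observation for one of them. A lesion that recurs early can be classified at once. A recurrence-free lesion can be classified only at year 5. Withdrawn recurrence-free lesions are left over, and the obvious crude treatments err in opposite directions. Counting them as recurrence-free lowers the rate, in the direction of success. Dropping them while keeping every observed recurrence raises it. The benchmark ranges with two ends are only 3 points (2-5%), 6 points (2-8%) and 4.7 points (1.7-6.4%) wide, so a rate set against them should be a 5-year rate.

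**Working it through.** **1. Duration.** Total duration = accrual period A + follow-up of the last patient (at least 5 years). The protocol gives no A, so its figure can be reproduced only with A = 0: 0 + 5 = 5 years. Assumed values of A = 1, 2 and 3 years give at least 6, 7 and 8 years. As follow-up per patient, 5 years matches the last scheduled visit.

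**2. Inputs for the rate.** From the protocol: the 5-year horizon, the benchmark ranges, 20-100 participants, and the remark that most excision recurrences fall within 2 years. Assumed:
- a true 5-year recurrence of p = 5%, with 2% and 8% as alternatives;
- a share L = 10, 20 or 30% withdrawn by year 5 at a constant rate, unrelated to recurrence;
- two timings of recurrence: a constant hazard, and a front-loaded curve with 70% of the 5-year recurrences spread evenly over years 0-2 and the rest evenly over years 2-5.

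The constant hazard puts (1 - 0.95^0.4)/0.05 = about 41% of recurrences in the first 2 years, which is less than most. It is kept as one end of the range because the timing after this treatment is unknown.

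**3. Formulas.** Withdrawal rate μ = -ln(1 - L)/5. Observed recurrences E = integral from 0 to 5 of f(t)·exp(-μt) dt, where f is the density of recurrence times. Lesions recurrence-free at year 5: C = (1 - p)(1 - L). Unclassified: 1 - E - C. The two crude rates are E (over all treated) and E/(E + C) (withdrawn dropped).

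**4. Worked case, p = 5%, L = 20%.** μ = 0.04463 and C = 0.95 × 0.80 = 76.0%.
- Constant hazard: λ = -ln(0.95)/5 = 0.01026. E = λ/(λ + μ) × (1 - 0.95 × 0.80) = 0.1869 × 0.24 = 4.49%. Dropping the withdrawn gives 4.49/(4.49 + 76.0) = 5.57%. Unclassified: 19.5%.
- Front-loaded: f = 0.0175 per year to year 2, then 0.005. E = 0.0175 × (1 - e^(-2μ))/μ + 0.005 × (e^(-2μ) - e^(-5μ))/μ = 3.35% + 1.28% = 4.63%. Dropping the withdrawn gives 5.75%. Unclassified: 19.4%.

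**5. All cases at p = 5%** (constant hazard / front-loaded):

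| Withdrawn | Recurrences over all treated | Withdrawn dropped |
|---|---|---|
| 10% | 4.75% / 4.82% | 5.26% / 5.34% |
| 20% | 4.49% / 4.63% | 5.57% / 5.75% |
| 30% | 4.21% / 4.43% | 5.96% / 6.25% |

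The first column is 0.2-0.8 point too low and the second 0.3-1.2 points too high. At a true 2% the errors are 0.1-0.3 and 0.1-0.5 point. At 8% they are 0.3-1.3 and 0.4-1.9 points.

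**6. Scale against chance.** With no withdrawals, the sampling SD of a 5% rate is √(0.05 × 0.95/n): 2.2 points for n = 100 and 4.9 for n = 20. In a simulation of 20,000 runs with 20% withdrawn and a full 5 years of follow-up for the rest, 1 minus Kaplan-Meier averaged 5.0%, with an SD of 2.3 points (n = 100) or 5.1-5.2 (n = 20). It removes the bias; it does not remove the imprecision.

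**The case against.** The case for leaving the text alone has four parts.

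- **The label is explained by its own next sentence.** Read together with the visit schedule, the 5 years is plainly follow-up per patient, and it is offered as an expectation. This stands: the fault is a loose label. It still needs correcting, because total duration is a protocol item and an analysis plan cannot restate it.
- **Estimator, censoring and denominators belong in a statistical analysis plan, which is not shown.** This stands as far as the absence of Kaplan-Meier goes; that absence is no finding. What remains is that the protocol itself fixes a two-way 5-year rule and a comparison with 5-year rates, and the rule cannot classify some lesions that the protocol expects to have.
- **Neither bias is written into the plan.** True. The protocol does not say that withdrawn lesions count as cured or that they are dropped. The figures above show what each choice would do, not what was chosen.
- **The effect is small.** True. It lies below sampling error, and the study-level criterion has no margin that a sub-point shift would cross.

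A reader might also infer from the 5-year label that the analysis will come 5 years after the first treatment, with later patients only partly followed. The documents do not support that. No early analysis is planned, every patient is to be tracked for at least 5 years, and the Ethics section keeps monitoring going even if the study is terminated. With that follow-up, late enrolment alone leaves no lesion unclassified; withdrawal does.

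**Conclusion.** The point holds in a narrow form and is minor. About 5 years is correct as follow-up per patient and cannot be the total study time under recruitment over time. The per-case rule leaves recurrence-free lesions withdrawn before year 5 unclassified, although the study-level rate is compared with 5-year rates.

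At a true 5% rate with 10-30% withdrawn, the error is 0.2-0.8 point too low or 0.3-1.2 points too high, depending on handling. The true rate, the withdrawal share and both recurrence timings are assumptions, as is withdrawal unrelated to recurrence. The error is systematic, and in the first case it favours the treatment. It is nevertheless smaller than the sampling SD of about 2.3 points at n = 100 and 5.2 at n = 20. A reader might infer that it could turn a failure into a success; nothing here shows that, and no change of conclusion is claimed.

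**What to change.** **Design, Selection Criteria, Data Source.** Label the 5 years as follow-up per patient. State the accrual period, and restate total duration as that period plus 5 years after the last treated patient.

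**Statistics.** Keep the per-case rule for lesions with 5 years of follow-up. Define the study-level rate as the 5-year cumulative recurrence from treatment by a time-to-event estimate (for example 1 minus Kaplan-Meier) with a 95% interval. Censor recurrence-free lesions at their last site examination. Allow for several lesions per patient where they occur, since the sample size counts participants and eligibility allows both cancers in one person. Show the number withdrawn beside the estimate. Further detail can go in the statistical analysis plan.

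**Cost.** Wording and a standard estimate. No new data are needed: Data Collection says "Each subsequent follow up visit will include data in the format of" recurrence or no recurrence, and withdrawals are already recorded. The downsides are a later stated end date, a possibly slightly less favourable rate, and the assumption that withdrawn lesions recur like those still followed. That assumption cannot be checked from the trial's data, which is why the number withdrawn must be shown.

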**Schedule of events/visits:**

-Visit #1: In office laser treatment

**\*\*For nodular/invasive carcinomas:**

**-Night of Visit #1: At home ointment application to treated site**

**-Night #2- Night #5: At home ointment application to treated site**

-For approximately 10-14 days following completion of ointment application: At home wound care performed twice a day at the treated site. Patients instructed to complete wound care until site is completely healed (for some could take up to 1 month)

1 month post-tx: Follow-up to check site (Take biopsy per patient consent)

6 month post-tx: Follow-up for complete skin exam and to check site

1 year: Follow-up for complete skin exam and to check site (Take biopsy per patient consent)

1.5 year: Follow-up for complete skin exam and to check site

2 years: Follow-up for complete skin exam and to check site (Take biopsy per patient consent)

2.5 year: Follow-up for complete skin exam and to check site

3 year: Follow-up for complete skin exam and to check site (Take biopsy per patient consent)

3.5 year: Follow-up for complete skin exam and to check site

4 year: Follow-up for complete skin exam and to check site (Take biopsy per patient consent)

4.5 year: Follow-up for complete skin exam and to check site

5 year: Follow-up for complete skin exam and to check site (Take biopsy per patient consent)

\*\*Advise biannual skin exam thereafter (always recommended to any patients with history of SCC/BCC skin cancer)

\*\*Advise return to office ASAP if abnormalities occur at site at any point in time

**Patient recruitment:** Established patients will be recruited if they develop biopsy confirmed SCC or BCCs. They will be given the option to participate in the study. For new patients, recruitment will be based on referrals by current patients or other physicians. Additionally, new patients may be recruited through the office website, social media, or other online marketing conducted by employees of [name].

**Patient retention:** Patients will be instructed of the importance of returning to the office for the scheduled follow ups. Patients will be closely tracked and monitored. We collect cell, home, mobile, and emergency numbers, emails, and addresses from all patients under our care. This provides multiple ways to contact patients. Patients will be instructed to make follow up appointments before leaving the office, if they don't then we will call when they are due. Patients are always called, texted, and/or emailed prior to their appointments to confirm. No show patients will be contacted multiple times. If no response is given after multiple electronic attempts, then letters are mailed to patients. These letters outline the importance of returning to the office for care and the risks associated with not returning.

**Patient criteria:** Participants must have a biopsy confirmed (by a pathologist or dermatopathologist) BCC and/or SCC and/or an hypertrophic actinic keratosis (solar keratosis) that extends to the base of a specimen and a BCC or SCC cannot be ruled out by the dermatopathologist. The carcinoma can be any level of invasiveness. Patients can be of any skin type, demographic, ethnicity or gender. The carcinoma cannot have been previously treated by any other means (surgical excision, laser, Mohs, electrodisssection, topical, etc.) Patients must be 18 years or older. Patients cannot be pregnant. We do not declare any other exclusion criteria in relation to previous or current diagnoses, surgeries, or medications.

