**Outcomes of interest:**

**primary**

1. Successful cure with the experimental method on all participants  
vs. clinical recurrence or worsening

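### The eligibility statements conflict on unconfirmed hypertrophic actinic keratoses, which on the plain reading enter a recurrence rate judged against carcinoma-only benchmarks

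*Protocol*

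**What the plan says.** **Who is eligible.** Under Design, Selection Criteria, Data Source, the Patient population paragraph states: "Patients must have a biopsy confirmed BCC and/or SCC skin cancer confirmed by a dermatopathologist". The Study Objective speaks of treating "previously biopsy-confirmed SCCs and BCCs", and Patient recruitment says "Established patients will be recruited if they develop biopsy confirmed SCC or BCCs". Patient criteria repeats the carcinoma requirement but extends it, by an and/or, to "an hypertrophic actinic keratosis (solar keratosis) that extends to the base of a specimen and a BCC or SCC cannot be ruled out". It then continues as if every lesion were a carcinoma: "The carcinoma can be any level of invasiveness".

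**What is counted.** The primary outcome is "Successful cure with the experimental method on all participants", set against clinical recurrence or worsening. The data collection section records each follow-up visit as "clinical recurrence or no clinical recurrence of carcinoma". In Statistics, for the single case, "treatment is considered effective if there is no clinical/histological recurrence in 5 years".

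**What it is compared with.** Statistics judges the study as a whole on its recurrence rate relative to established treatments. The 5-year surgical excision figures given are 2% to 5% for superficial BCC, 2% to 8% for nodular BCC, about 0.8% for SCC in situ and 1.7% to 6.4% for invasive SCC. There is no control group. The planned size is 20 to 100 participants.

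**The concern.** A hypertrophic actinic keratosis in which carcinoma has merely not been excluded is a lesion of unresolved diagnosis. The Rationale itself treats actinic keratosis as something that may progress to carcinoma, and so as distinct from it. One eligibility statement shuts out a patient who has only such a lesion, and the other lets that patient in.

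This reaches the analysis because the external comparison is the study's only test of effectiveness. With no concurrent control, the treated lesions need to be of the kind that the benchmarks describe. If unresolved lesions recur less often than confirmed carcinomas, including them lowers the overall rate and favours the method. More participants would not remove that mismatch.

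**Working it through.** **Step 1: eligibility, side by side, for a patient with only an unresolved keratosis.**

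| Protocol section | Eligible? |
|---|---|
| Patient population | No: confirmed carcinoma is mandatory |
| Study Objective | Not described |
| Patient recruitment (established patients) | Not described |
| Patient criteria | Yes |

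The direct conflict is between Patient population and Patient criteria. The other two sections agree with the narrower rule, but neither is itself an eligibility criterion.

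**Step 2: does such a patient enter the benchmarked rate?** The primary outcome covers all participants and the success rule concerns the whole study. The protocol takes these patients out of neither. Each benchmark belongs to a BCC or SCC type, so none applies to them. On the plain reading they are in the rate.

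**Step 3: possible size.** There is no planning figure to reproduce: the 20 to 100 participants are a feasibility estimate without power, effect size or margin. For illustration, let p be the recurrence rate in confirmed carcinomas, f the share of participants with only an unresolved keratosis, and r their recurrence rate relative to p. Then

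pooled rate = p × [(1 − f) + f × r].

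The values of p are taken from the quoted benchmarks (0.8%, 2%, 8%). Both f and r are assumptions. With f = 20%:

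| p | r = 0 | r = 0.5 | r = 1 | r = 1.5 |
|---|---|---|---|---|
| 8% | 6.4% | 7.2% | 8% | 8.8% |
| 2% | 1.6% | 1.8% | 2% | 2.2% |
| 0.8% | 0.64% | 0.72% | 0.8% | 0.88% |

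For example, 8% × (0.8 + 0.2 × 0) = 6.4%, and 8% × (0.8 + 0.2 × 1.5) = 8.8%. Over f = 10%, 20% and 30% with r = 0, a true 8% becomes 7.2%, 6.4% and 5.6%, and a true 2% becomes 1.8%, 1.6% and 1.4%.

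**Step 4: the shift against sampling error.** With SE = √[p(1 − p)/n] and p = 8%:

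- n = 20: SE = √(0.08 × 0.92/20) = 6.07 points. The shift of 1.6 points is 1.6/6.07 = 0.26 SE. Expected recurrences fall from 1.6 to 1.28.
- n = 100: SE = √(0.08 × 0.92/100) = 2.71 points. The shift is 1.6/2.71 = 0.59 SE. Expected recurrences fall from 8 to 6.4.

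**The case against.** **The comparison may be meant type by type.** Statistics refers to comparison groups and to recurrence rates in the plural, lists benchmarks by type, and defines subgroups by cancer type and invasiveness. Read that way, a keratosis matches no benchmark and drops out. This stands as an alternative reading and limits confidence in the pooled one. It does not displace the sentence that judges the study as a whole on its recurrence rate.

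**An analysis plan could define the analysis set.** It could, and the absence of a keratosis stratum is not by itself a fault of the protocol. But an analysis plan cannot reconcile two eligibility statements in the protocol, and the protocol itself sets the primary outcome on all participants.

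**Keeping everyone treated in the result is defensible.** Agreed. That is a reason to go on reporting the all-participants result, but not to judge it by carcinoma figures. It is also true that a confirmed-carcinoma rate would still pool types with benchmarks from 0.8% to 8%, so the restriction removes one mismatch and not all of them.

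**Stronger readings that the protocol does not support.**

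- A reader might infer that a keratosis counts as a success whenever no carcinoma appears. The primary outcome also names worsening as a failure, and the per-case rule in Statistics does not limit recurrence to carcinoma; that qualifier comes from the visit-recording description.
- A reader might infer that the study would pass wrongly. With an assumed true carcinoma rate of 10%, no recurrences in keratoses and a cut-off of 8%, the chance of an observed rate at or below 8% with 100 participants rises from 0.32 to 0.59 at a 20% keratosis share. Every one of those inputs is assumed, and the protocol sets no numeric cut-off.
- A reader might infer that the bias must favour the method. Some of these lesions reach the specimen base and may hold unsampled carcinoma, so the effect could be nil or run the other way.

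**Conclusion.** The concern holds in two parts. The eligibility conflict between Patient population and Patient criteria is plain on the page, and confidence in it is high. That these lesions enter the benchmarked comparison is the plain reading of the study-level rule but not the only one, and confidence there is moderate.

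The consequence for the result cannot be sized from the protocol, because it gives neither the share of keratosis-only participants nor their recurrence rate. The illustrated shift needs both a 20% share and complete absence of recurrence in these lesions, and even then stays below one standard error at either end of the planned size. No crossing of a threshold is claimed. The point should still be acted on, because the external comparison carries the whole conclusion and the repair is cheap.

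**What to change.** 1. Reconcile Patient population and Patient criteria on whether a patient with only an unresolved hypertrophic actinic keratosis may enter, and align Study Objective and Patient recruitment with the answer.
2. If these lesions remain eligible, base the recurrence rate that is compared with the carcinoma benchmarks on participants with biopsy-confirmed BCC or SCC. A participant with both kinds of lesion stays in through the carcinoma.
3. Report keratosis-only participants separately and descriptively: their number, recurrence or worsening, and any carcinoma later found at the site.
4. Still report the all-participants result, but do not set it against the carcinoma benchmarks.

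**Cost.** This changes the set behind the benchmarked rate, so it is more than a wording edit. No new data are needed, because eligibility already depends on the entry biopsy diagnosis. The denominator becomes smaller. At an assumed 20% share it is 16 instead of 20, or 80 instead of 100. The standard error of an 8% rate then rises from 6.1 to 6.8 points (√(0.08 × 0.92/16)), or from 2.7 to 3.0 points (√(0.08 × 0.92/80)). For a 2% rate it rises from 3.1 to 3.5 points, or from 1.4 to 1.6.

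### Carcinomas already cleared by their diagnostic biopsy are eligible and count as cures by the laser and ointment, which inflates the absolute cure rate by an unknown amount

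*Protocol*

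**What the plan says.** **Eligibility.** Under Design, Selection Criteria, Data Source, the Protocol states that "Patients must have a biopsy confirmed BCC and/or SCC skin cancer". Patient criteria adds a keratosis route, for a "hypertrophic actinic keratosis (solar keratosis) that extends to the base of a specimen" in which the dermatopathologist is unable to exclude a BCC or SCC. For carcinomas it says "The carcinoma can be any level of invasiveness" and sets no condition on what the specimen shows at its base or edges.

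**Exclusions.** "The carcinoma cannot have been previously treated by any other means"; the examples given include surgical excision and topical treatment, and the list is open-ended. The diagnostic biopsy is not named. The section then adds: "We do not declare any other exclusion criteria in relation to previous or current diagnoses, surgeries, or medications".

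**Data.** Data Collection/Data Management lists the data taken at initial treatment: demographics, lesion location, invasiveness and treatment settings. It also leaves room for further data as needed. Base or margin status is not named.

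**Analysis.** Statistics defines subgroups by cancer type, invasiveness, skin type and gender. A case counts as effective if nothing recurs clinically or histologically over 5 years. Outcomes of interest attributes that cure to the experimental method. Statistics also states that there is no control group.

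**The concern.** Every lesion is biopsied before it is treated, and a biopsy removes tissue. Some carcinomas, particularly small or superficial ones, may have little or no tumour left when the laser is applied. Such a lesion is eligible, is unlikely to recur whatever is done next, and is then scored as cured by the laser and ointment. With no control group, nothing in the design separates the work of the biopsy from that of the treatment.

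What is at stake is the meaning of the headline result. A reader will take the cure rate as the chance that the method eradicates a carcinoma that is present. As defined, it is a mixture of that chance and the share of lesions with nothing left to treat. The Protocol's section on potential bias names selection, attrition and reporting bias, but not this one.

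**Working it through.** The Protocol derives no figure that can be reproduced here: the 20–100 participants come from office caseload. The check is therefore a reading of the text followed by an illustration of size.

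**Step 1: trace one lesion through the plan.** Take a BCC whose diagnostic specimen has a clear base and clear margins.
- Patient criteria: eligible, since it is biopsy-confirmed and any invasiveness is allowed.
- Prior-treatment exclusion: not clearly triggered, since the biopsy is itself required and is not named.
- Listed baseline data and subgroups: nothing marks it as different from a lesion with tumour at the base.
- Outcome: no recurrence by 5 years, so it is scored as a cure by the method.

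**Step 2: model.** Let f be the share of lesions already cleared by biopsy (recurrence assumed zero) and r the 5-year recurrence rate in lesions with residual tumour. Then

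observed rate = (1 − f) × r.

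Both f and r are assumptions, because the documents give neither.

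**Step 3: share needed to bring r down to a benchmark b.** f = 1 − b/r, where b is the upper figure that Statistics quotes for surgical excision (a single figure for SCC in situ).

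| Benchmark | b | r = 10% | r = 12% | r = 16% | r = 20% |
|---|---|---|---|---|---|
| Nodular BCC | 8% | 20% | 33% | 50% | 60% |
| Invasive SCC | 6.4% | 36% | 47% | 60% | 68% |
| Superficial BCC | 5% | 50% | 58% | 69% | 75% |
| SCC in situ | 0.8% | 92% | 93% | 95% | 96% |

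For example, at r = 12%: 1 − 0.08/0.12 = 0.333 and 1 − 0.008/0.12 = 0.933. Only the most lenient benchmark is reached at a moderate f.

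**Step 4: the same relation in reverse.** r = observed/(1 − f). An observed 8% corresponds to r = 8.9% (f = 10%), 10.0% (20%), 11.4% (30%) or 16.0% (50%).

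**Step 5: precision if no recurrence is seen.** Assume one lesion per participant. With 0 recurrences in 20, the one-sided 95% upper bound is 1 − 0.05^(1/20) = 13.9% over all lesions. For lesions with residual tumour, the denominator falls to 20 × (1 − f). That gives 1 − 0.05^(1/16) = 17.1% at f = 20% and 1 − 0.05^(1/10) = 25.9% at f = 50%. With 0 in 100, the bounds are 3.0%, 3.7% and 5.8%.

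**Step 6: comparison with published rates.** Suppose the published series contain the same share f, with residual-tumour rates r_T here and r_B there. The ratio (1 − f)r_T / (1 − f)r_B = r_T/r_B does not change. The difference becomes (1 − f)(r_T − r_B). With r_T = 12%, r_B = 8% and f = one third, the observed rates are 8.0% and 5.3%. The ratio stays at 1.5, and the difference falls from 4.0 to 2.7 percentage points. If the published series carry less dilution than this study, the comparison favours the treatment; if more, it works against it. The documents do not say which holds.

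**The case against.** **The keratosis clause is about diagnosis.** Read whole, it explains how a lesion without a carcinoma diagnosis can qualify: it runs to the base of the specimen, so carcinoma cannot be excluded. A reader might infer that the sponsor set a residual-disease requirement and left it off carcinomas. The text does not support that, and the point does not depend on it.

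**An SAP may deal with it.** A reader might infer that base status will play no part in any analysis. That cannot be established without the SAP, and the Protocol does allow further data to be collected. What stands is narrower: the Protocol fixes eligibility and the success definition, and its list of baseline data omits the variable. An analysis by base status needs that field to be collected.

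**The prior-treatment exclusion may cover an excisional biopsy.** The mention of surgical excision and the open-ended list permit that reading. It is not stated, and it would not reach a partial biopsy that happened to clear the lesion.

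**The sizes are assumed.** This is correct. Nothing in the documents shows that biopsies clear a material share of carcinomas, and r = 12% has no source. The 33% threshold applies only to the most lenient benchmark.

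**The published series may share the effect.** This also stands, and it rules out any claim about the direction of bias in the benchmark comparison.

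**Conclusion.** The concern holds for the absolute cure rate. As written, a carcinoma already cleared by its biopsy can be enrolled and, if it does not recur, is credited to the laser and ointment, with no control group to offset this. The direction of that effect is clear: the cure rate overstates what the method does to residual tumour whenever f is above zero. Its size is unknown. Under the assumed r of 12%, f must be about 33%, 47%, 58% and 93% to reach the 8%, 6.4%, 5% and 0.8% benchmarks; other values of r move these thresholds as tabulated. The model also assumes that cleared lesions never recur.

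A reader might go further and infer that the comparison with published treatments is biased in favour of the method. The documents do not support that. They say nothing about biopsy clearance in the published series, and an equal share there leaves the ratio of rates unchanged and shrinks only the absolute difference. This is a low-cost gain in interpretability and does not show that the planned comparison is wrong.

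**What to change.** Leave eligibility unchanged. Add one item to the baseline data in Data Collection/Data Management: whether tumour reaches the base or margin of the diagnostic specimen (yes / no / not stated), taken from the pathology report that enrolment already requires. In Statistics, state that the 5-year recurrence rate with its confidence interval will be reported for lesions with tumour at the base or margin, beside the all-lesion rate, with the number of lesions in each of the three categories.

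The cost is one field and one table. Some reports will not state base or margin status. With 20–100 participants over several tumour types, the involved subset will be small and its interval wide. Specimen status is also only a proxy for residual tumour, so the table aids interpretation but does not estimate f exactly.
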